Study objectives	
Primary Objective
 
Absolute pain score 24h after surgery, assessed by 100mm visual analogue score (VAS).
 
Secondary Objectives
 
Minimal Clinically Important Difference [MCID] in visual analogue score; VAS adjusted for pain severity; postoperative morbidity; opioid use; heart rate variability [explanatory variable].

Study design	Phase II, single-centre, two-arm, parallel group randomised controlled trial
Setting	Surgical services of hospitals undertaking major trauma orthopaedic surgery.
Participants	
Inclusion criteria
 
 • Scheduled to undergo major elective or urgent (not requiring intervention in <24h) noncardiac (orthopaedic) surgery under general and/or spinal anaesthesia, expected to take >120 minutes from the induction of anaesthesia. • American society of Anaesthesiologists (ASA) grade I–III. • Aged 18 years and over. 
Exclusion criteria
 
 • Requiring invasive mechanical ventilation and/or new renal replacement therapy during hospitalization. • Cardiac arrhythmia requiring therapy prior to/during hospitalization. • Dementia. • Cancer requiring active/ongoing therapy. • Postural orthostatic tachycardia syndrome. • Lower limb neuromuscular disorders. • Auricular dermatitis. • Day-case surgery, not requiring overnight hospital admission.
Interventions	
Sham Group: Patients randomised to receive sham treatment will receive no current via the bilateral auricular leads for 50 minutes.
 
Stimulation Group: Patients randomised to receive stimulation will receive a sub-threshold current via the bilateral auricular leads for 50 minutes.

Primary outcome measure	The primary outcome is absolute pain score 24h after surgery, assessed using the 100mm visual analogue score.

Outcome measures

Primary outcome measure

The primary outcome will be the absolute VAS pain score 24h after surgery.

Secondary outcome measures

Minimally Clinical Important Difference: The proportion of participants who achieve a minimally clinical relevant reduction >10mm using the 100 mm pain Visual Analogue Score will be compared before and after the period of stimulation in each group, before and after surgery.[1]

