VAS stratified by pain intensity: Absolute changes in pain score before and after sham/stimulation will be compared before and after the period of stimulation in each group before and after surgery, stratifying for mild, moderate, and severe pain intensity before the intervention. A pain VAS score of 30, 70, and 100 indicates the upper boundaries of mild, moderate, and severe pain intensity.[1]

Postoperative morbidity: Defined by the Post Operative Morbidity Survey (POMS) before (preoperative) and after (postoperative days 3 and 7) surgery. The POMS is an 18-item survey which examines nine domains (pulmonary, infection, renal, gastrointestinal, cardiovascular, neurological, haematological, wound, pain) of postoperative morbidity.[2] The POMS is a reliable and valid measure of short-term postoperative morbidity following major surgery.²⁰ The hospital electronic patient management system will be used to prospectively record POMS on postoperative days 0 (preoperative), 3 and 7. Clavien-Dindo grades for complications during hospital stay will also be reported.

Opiate use: Opiate consumption [expressed as morphine equivalents] before and for three days after surgery.

Explanatory measures

Autonomic function, as assessed by time and frequency domain measures of heart rate variability 10 minutes before and 10 minutes after each stimulation session, before and after surgery.[3]

Sample size and randomisation

Sample size calculation

Consensus perioperative guidelines recommend that the Visual Analogue Score should be used to assess pain intensity.[4] 72 patients are required to have a 90% chance of detecting, significant at the 1% level, a decrease in mean VAS (the primary outcome measure) from 34mm in the control group to 23mm in the experimental group after surgery (standard deviation of outcome 12mm). Allowing for 10% dropout per group, a final sample size of 86 participants is required, analysed by intention to treat.

Randomisation procedure

Randomisation will occur after the participant has provided informed consent before the surgical procedure is due to start. Participants are randomly assigned (1:1) by block randomisation to receive stimulation or sham stimulation to ensure a balance in sample size across groups over time (Power

Analysis & Sample Size (PASS) 2021, Utah, USA). Investigators will log on to a secure web-based randomisation file to obtain a unique patient identification number and allocation to a treatment group.

Analysis methods

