General analysis principles

Analyses will follow the intention-to-treat principle: all randomised patients with a recorded outcome will be included in the analysis and analysed according to the treatment to which they were randomised [5, 6]. Patients will be included in the analysis, regardless of whether the treatment they received was compliant with the protocol. Definitions of what constitutes a recorded outcome for each outcome can be found in Appendix 1. Patients with missing outcome data will be excluded from the analysis. Missing data for baseline covariates to be included in the analysis model will be accounted for using mean imputation for continuous variables and the missing indicator approach will be used for missing data for categorical variables [7, 8].

For the analysis of the primary outcome, each secondary outcome, and all process measures, we will present the following information:

The number of patients included in each analysis, by treatment group

A summary statistic of the outcome (e.g. mean (SD), number (%)), by treatment group

The estimated treatment effect

A 95% confidence interval for the estimated treatment effect

A two-sided p-value

For all analyses, a significance level of 5% will be used.

Representativeness of patients

A log of eligible patients not recruited to the trial will be kept. Reasons for non-participation will be categorised and summarised. Participation in the trial, treatment allocation and completeness of follow-up will be illustrated by a CONSORT flow diagram [9].

Baseline characteristics

Baseline characteristics will be summarised for each treatment group by the mean and standard deviation or median and interquartile range for continuous variables, and the number and percent for categorical variables. The following baseline characteristics will be summarised by treatment group:

- Demographic: age (years), gender (male/female)
- Co-morbid disease: Hypertension; Ischaemic heart disease; Cardiac failure; Cardiac valvular disease
- Stroke/TIA; Peripheral vascular disease; Diabetes mellitus, type I; Diabetes mellitus, type II ; COPD; Asthma
Smoker; Interstitial or other respiratory disease; Liver cirrhosis; GI pathology-other; Osteoarthritis;
Rheumatoid arthritis; Inflammatory disease; Active cancer; Previous cancer
- ASA grade

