The effect of stimulation/sham on time and frequency domain measures of heart rate variability 10 minutes before and 10 minutes after each stimulation session, before and after surgery.[3] . Repeat-

measures ANOVA will be used (group: stimulation/sham X experimental timepoint X before/after surgery), with post hoc Tukey-Kramer testing.

Exploratory analyses

Exploratory analyses will be repeated to examine the relationship between autonomic parameters and achieving MCID, independent of group allocation to stimulation/sham.

Sensitivity analysis

The amount of missing primary outcome data is anticipated to be minimal but will be accounted for in a sensitivity analysis if missing data is greater than 5%.

Other analyses, data summaries and graphs

Clinical management

Clinical management for sham/stimulation groups will be summarised but not subjected to statistical testing. Numbers (%) and means (SD) or medians (IQR) will be provided separately for each group. The sham/stimulation groups will be compared for the following clinical management characteristics:

- Anaesthetic technique
- level of care on the first night after surgery

Process measures

Summary measures will be presented separately for each treatment group. All patients with recorded data will be included in the summary. Formal statistical analysis will not be performed. Duration of hospital stay after surgery (days) will be summarised using median (IQR).

Safety analyses

Adverse events and serious adverse events will be presented as a number (%) by treatment group. All patients with a recorded outcome will be included in the summary. In addition to this, 'other' adverse events will be reported separately if prevalence is more than 5% across all participants in the trial.

- Arrhythmia
- Headache
- Pain
- Skin irritation at the stimulation site
- Dizziness
- Other
- None

Protocol deviations

Numbers and percentages of protocol deviations will be reported. Protocol deviations will be reported as participants who stopped therapy either during the stimulation period, before and/or after surgery. Stimulation current, as applicable, will be reported to demonstrate variation in protocol parameters.

Complications within 30 days after surgery

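### The Tukey-Kramer follow-up to the HRV analysis, in its standard single-error form, cannot fit both the arm-versus-arm and the within-patient comparisons, and the SAP does not name the valid interaction test

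*SAP*

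**What the plan says.** The design is a "Phase II, single-centre, two-arm, parallel group randomised controlled trial" (SAP, study summary table, Study design). Under Randomisation procedure, "Participants are randomly assigned (1:1) by block randomisation to receive stimulation or sham stimulation". The first Explanatory measures section, under Outcome measures, defines the endpoint: "Autonomic function, as assessed by time and frequency domain measures of heart rate variability 10 minutes before and 10 minutes after each stimulation session". The second, under Analysis methods, repeats the schedule as "heart rate variability 10 minutes before and 10 minutes after each stimulation session, before and after surgery" and then gives the method: "measures ANOVA will be used (group: stimulation/sham X experimental timepoint X before/after surgery), with post hoc Tukey-Kramer testing".

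The SAP does not say which means the post hoc tests compare, which error term they use, or which term of the ANOVA is the test of stimulation on HRV. Under General analysis principles, "For all analyses, a significance level of 5% will be used". The Study objectives row lists HRV among the secondary objectives but tags it: "heart rate variability [explanatory variable".

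**The concern.** Each patient belongs to one arm and gives four HRV readings: before and after a session, before and after surgery. Crossing arm with reading gives eight cell means. Some pairs of means come from different patients and are independent. Others come from the same patients and are correlated. Tukey-Kramer in its standard form treats all means as independent with one common error variance, so it does not match this layout.

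HRV is the only autonomic measure in the SAP, so these comparisons would be read as evidence on whether stimulation changes autonomic function. Depending on an error term that the SAP leaves open, the same data could show a false arm difference or miss a real one. In addition, no single pair among the eight means is the between-arm difference in the change from before to after a session.

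**Working it through.** **Inputs from the SAP.** There are two arms and four readings per patient, taking the experimental timepoint factor as before and after a session. That gives 2 × 2 × 2 = 8 cell means and 8 × 7 / 2 = 28 pairs, of which 4 compare the arms at the same reading. The SAP gives no power or error rate for HRV. The numbers per arm come from the VAS calculation: "72 patients are required to have a 90% chance of detecting, significant at the 1% level, a decrease in mean VAS". That figure reproduces: 2 × (2.576 + 1.282)² × 12² / 11² = 35.4, so 36 per arm and 72 in all. The final size of 86 gives 43 per arm. I use 36 and 43.

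**Assumptions not in the SAP.** Normal data with common SD σ, equal correlation ρ between any two readings of a patient (0.3 to 0.8), and Tukey-Kramer applied to all eight means.

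**Variances that the comparisons need.**
- Arm versus arm at one reading: 2σ²/n.
- Before versus after within an arm: 2σ²(1−ρ)/n.

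These are equal only if ρ = 0.

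**What each error mean square estimates.**
- Within-patient: σ²(1−ρ).
- Between-patient: σ²(1+3ρ).
- Pooled over all cells (one part between, three parts within): [σ²(1+3ρ) + 3σ²(1−ρ)] / 4 = σ².

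**(a) Within-patient error.** This suits the paired comparisons but is too small for the arm comparisons. The Tukey critical value for eight means is about 3.06 (studentized range / √2). For an arm pair it shrinks to 3.06 × √(1−ρ):

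| ρ | Effective critical value | False positive, one arm pair | At least one of the 4 same-time arm pairs (simulated) |
|---|---|---|---|
| 0.3 | 2.56 | 1.0% | about 4% |
| 0.5 | 2.16 | 3.0% | about 10% (9-11%) |
| 0.7 | 1.68 | 9.4% | about 23% (21-24%) |
| 0.8 | 1.37 | 17% | about 33% (32-36%) |

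The ranges cover separate simulations at 36 and 43 per arm. The intended 5% is for all 28 pairs together.

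**(b) Pooled error.** The arm comparisons then have the correct variance, 2σ²/n, and the cost is the 28-pair correction. For a 0.5 SD arm difference the standardised effect is 0.5 / √(2/36) = 2.12, or 0.5 / √(2/43) = 2.32. Against a critical value of 3.05, power is Φ(2.12 − 3.05) = 18% and Φ(2.32 − 3.05) = 23%; simulation gives 18-24% over all ρ. The same pair tested alone at 5% has about 55% and 63%.

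Only the within-arm pairs get a wrong variance, and it is too large. At ρ = 0.5 a 0.5 SD change has power Φ((2.12 − 3.05) / √0.5) = 9% and Φ((2.32 − 3.05) / √0.5) = 15%; simulation gives 10% and 15%.

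**(c) Between-patient error.** This is too large for every pair when ρ > 0. For a 0.66 SD arm difference at ρ = 0.5 and 36 per arm, simulated power is 2.5%, against 79% for a two-sample t-test.

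**(d) The ANOVA's own interaction.** The group by timepoint test, simulated at 36 per arm, has a type I error of 4.8-5.0%. For a 0.66 SD shift after each session its power is 91% at ρ = 0.3, 97% at 0.5 and above 99% at 0.7 or more.

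**The case against.** The best defence is that the SAP has not chosen a wrong error term. It names none, does not say that all eight means are compared, and does not mention 28 pairs. The named software may run the post hoc tests term by term with each term's own error; the documents do not settle this. The mixed ANOVA itself separates between- and within-patient error, and its group by timepoint interaction tests the effect of interest validly. HRV is also absent from the primary and secondary outcomes table (Appendix 3, Table 4). All of this stands. It limits the point to the post hoc step and makes the error rates in (a) conditional. It does not remove the point, because the only follow-up the SAP names does not fit the design in its standard form, and the interaction that would serve is not identified as the test.

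Two stronger readings are tempting. One is that the arm comparisons will have inflated error. The SAP does not support that as a certainty: it holds only with the within-patient error, and at ρ = 0.3 the rate is no higher than 5%. The other is that a single error variance costs the arm comparisons most of their power. Under a pooled error that is wrong, because the arm variance is then correct and the loss comes from correcting for 28 pairs. The loss also depends on effect size: at 0.66 SD and 36 per arm, power is about 40% against 79%, so about half is lost.

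**Conclusion.** The point holds for the post hoc step of the HRV analysis only. No single error mean square serves both kinds of comparison, and the SAP leaves the choice open. The consequence ranges from a false-positive chance of about 4% to 33% over the four same-time arm comparisons (within-patient error, ρ from 0.3 to 0.8) to power of 18-24% for a 0.5 SD arm difference (pooled error, through the multiplicity correction). These figures rest on assumed correlations, equal correlation between readings, normal data and testing of all eight means.

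A reader might infer that the whole HRV analysis, or the trial's main conclusion, is unsound. Neither follows. The ANOVA F tests are unaffected, and HRV is explanatory, so the primary conclusion is not touched through this section. The change is worth making before analysis, but it is not critical.

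**What to change.** In the HRV analysis under Explanatory measures:

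1. Remove the Tukey-Kramer step.
2. Name the group by timepoint interaction, with its further interaction with surgery, as the overall test of stimulation on HRV.
3. Report two prespecified between-arm contrasts with 95% CIs, from a mixed model with an unstructured covariance over each patient's four readings, so that each contrast has its own standard error: (i) the preoperative post-session reading and (ii) the postoperative post-session reading. Adjust both for the preoperative pre-session reading. The postoperative pre-session reading is not a baseline, because it follows the first randomised session.
4. Apply Holm over the two contrasts for each HRV measure, and present results across the several time and frequency domain measures as explanatory.

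The cost is SAP wording and a slightly different model specification, with no new data. The small downside is that the other pairwise comparisons are no longer tested.

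### The SAP does not define a recorded heart rate variability outcome, so its patient-level exclusion rule and four-recording repeated-measures ANOVA could discard valid preoperative data

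*SAP*

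**What the plan says.** Both Explanatory measures paragraphs of the SAP (under Outcome measures and under Analysis methods) describe "heart rate variability 10 minutes before and 10 minutes after each stimulation session, before and after surgery". That makes four recordings per patient: before and after a session, on each side of surgery. The analysis is a single three-factor repeated-measures model: "measures ANOVA will be used (group: stimulation/sham X experimental timepoint X before/after surgery".

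General analysis principles sets the missing-data rule in three sentences. The first is inclusive: "all randomised patients with a recorded outcome will be included in the analysis". The second excludes: "Patients with missing outcome data will be excluded from the analysis". The third says where the detail is: "Definitions of what constitutes a recorded outcome for each outcome can be found in Appendix 1". Appendix 1 then lists the primary outcome and four secondary outcomes, and does not mention HRV.

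The Sensitivity analysis section is confined to the primary outcome: "The amount of missing primary outcome data is anticipated to be minimal but will be accounted for in a sensitivity analysis", triggered above 5% missing. Protocol deviations anticipates incomplete treatment, counting "participants who stopped therapy either during the stimulation period, before and/or after surgery".

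**The concern.** A classical repeated-measures ANOVA with two within-patient factors needs all four cells from each patient. If the exclusion rule is applied to the patient, a failed trace or a cancelled postoperative session also removes that patient's complete preoperative pair.

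The preoperative session is the cleanest look at whether stimulation changes autonomic function, because surgery, anaesthesia and postoperative opioids have not yet acted. Its sample should not depend on what happens after the operation. If postoperative loss is related to how the patient is doing, the retained patients are a selected group. Even if it is not, usable data are thrown away. The same autonomic parameters also feed the exploratory analysis of who reaches the MCID.

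**Working it through.** **Plan's own figure.** There is none for HRV: no sample size, power or loss rate. The only sizes are for the VAS comparison (72 evaluable, 86 randomised, 10% dropout). I use 86, or 43 per arm, as the base. Every HRV loss rate below is an assumption.

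**Step 1: patients dropped if all four recordings are required.** Let q be the chance that a recording is lost.
- Independent losses: share dropped = 1 − (1 − q)^4.
- Both recordings of a session lost together: share dropped = 1 − (1 − q)^2.

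| q (assumed) | Dropped, clustered by session | Dropped, independent | Complete cases of 86 (clustered / independent) |
|---|---|---|---|
| 1% | 2% | 4% | 84.3 / 82.6 |
| 5% | 10% | 19% | 77.6 / 70.0 |
| 10% | 19% | 34% | 69.7 / 56.4 |

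If all four recordings of a patient are lost together, the share dropped is only q and no obtained recording is wasted.

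**Step 2: effect on the preoperative pair.** Suppose 10% of patients have no postoperative session (borrowing the SAP's dropout figure) and single recordings also fail independently.
- At 5%: intact preoperative pair 0.95^2 = 90%; all four recordings 0.9 × 0.95^4 = 73%.
- At 10%: intact preoperative pair 0.90^2 = 81%; all four recordings 0.9 × 0.90^4 = 59%.

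So 17 and 22 percentage points of patients with a usable preoperative pair would be set aside.

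**Step 3: power.** The simulations assume 43 per arm, correlation 0.7 between any two recordings, a 0.35 SD rise in both post-session recordings under stimulation, losses at random, and a 5% test of group by timepoint.

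| Loss pattern (assumed) | Complete-case power | All-available power |
|---|---|---|
| 1% clustered by session | 0.82 | 0.83 |
| 2% clustered by session | 0.83 | 0.84 |
| 5% clustered by session | 0.79 | 0.82 |
| 10% miss postoperative session + 5% independent | 0.70 | 0.78-0.79 |
| 10% miss postoperative session + 10% independent | 0.61-0.62 | 0.74-0.77 |

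The ranges in the last two rows reflect separate simulations, using either a mixed model or all available session changes. With a 0.5 SD effect, the fourth row becomes 0.95 against 0.97.

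**Step 4: which all-available model.** A mixed model with only a random patient intercept assumes that all four recordings are equally correlated. Suppose instead the correlation is 0.8 within a session and 0.5 between sessions, with unit variance and contrast weights of ±1/2.
- Timepoint contrast variance: (4 − 4 × 0.8)/4 = 0.2. The timepoint-by-surgery contrast has the same variance.
- Before/after-surgery contrast variance: (4 + 4 × 0.8 − 8 × 0.5)/4 = 0.8.
- The random-intercept model pools these to (0.2 + 0.8 + 0.2)/3 = 0.4.

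Its nominal 1.96 cut-off then acts as 1.96 × √(0.4/0.2) = 2.77 for group by timepoint and 1.96 × √(0.4/0.8) = 1.39 for group by surgery. The true two-sided error rates are about 0.6% and 17%, not 5%. Null simulations agree (0.6-0.7% and 16-17%).

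**The case against.** The strongest reply is that the SAP never says a patient needs all four recordings. The inclusive sentence in General analysis principles can be read as keeping anyone with some HRV data. This stands: listwise deletion is an inference from the exclusion sentence and the usual form of the named ANOVA. But the inclusive reading does not settle the analysis. Nothing says whether one, two or three recordings count, or how the ANOVA would use them. The SAP says the definition is in Appendix 1, where it is absent, so this is not a detail left to the protocol.

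A reader might infer that much of the HRV sample will be lost. The document does not support that. It gives no loss rate, and the loss is small at 1% per recording or when losses cluster. The less favourable simulations add single-trace failures to a dropout allowance that was made for the VAS outcome.

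A reader might also infer that the HRV result will be biased by selective loss. The simulations drop data at random and so do not measure selection. The exclusion criteria already name arrhythmia requiring therapy, invasive ventilation and day-case surgery, which narrows some routes to selective loss. Selection remains a reason for care, not a demonstrated effect.

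Finally, HRV is an explanatory variable and does not appear in Table 4. That limits the importance of the point.

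**Conclusion.** The point holds in a limited form. The SAP leaves partial HRV data undefined, and its most natural reading could discard valid preoperative pairs because of later losses. The share of patients dropped is about 2-4%, 10-19% or 19-34% at an assumed 1%, 5% or 10% loss per recording. The power cost runs from about 1 to 3 points at 1-5% session-clustered loss to about 8 to 15 points in the less favourable scenarios. It shrinks if the true effect is larger than the assumed 0.35 SD.

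These figures rest on assumed loss rates, correlation and effect size, none of which the SAP supplies. The primary conclusion is untouched. This is an inexpensive improvement of minor to moderate importance.

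**What to change.** 1. Add an HRV entry to Appendix 1 that defines a recorded outcome, and state that for HRV the exclusion rule applies per recording or per session, not per patient.
2. Replace the repeated-measures ANOVA for HRV with an analysis that uses the available recordings. There are two suitable options:
   - **Session-wise comparison:** compare post-session HRV by arm, adjusted for pre-session HRV, separately before and after surgery. Postoperative losses then cannot affect the preoperative result. A patient still needs both recordings of the session analysed, and there is no direct test of whether the effect differs across surgery.
   - **Mixed model for repeated measures:** fit arm, timepoint, before/after surgery and their interactions, with an unstructured covariance over the four recordings. Patient and patient-by-session random effects, plus patient-by-timepoint if needed, are an alternative. A random patient intercept alone should not be used, for the reason in step 4 of the working.
3. Report the number of usable recordings by arm, session and timepoint.

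The cost is SAP wording, a little more analysis work and a check that the named software fits the chosen model. No further patients or measurements are needed. The mixed model relies on data being missing at random given the observed recordings, which is weaker than what a complete-case analysis assumes but still cannot be verified.

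### The heart rate variability ANOVA treats the recording made before any stimulation as an outcome, so the preoperative-session effect is an unadjusted change score where baseline adjustment would be more precise

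*SAP*

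**What the plan says.** The outcome section of the SAP (Explanatory measures) sets the recordings: "heart rate variability 10 minutes before and 10 minutes after each stimulation session, before and after surgery". I read this as one session before and one after surgery, hence four recordings per patient. Table 3, with one row for current before and one for current after, fits that reading.

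The analysis section (also headed Explanatory measures) gives the model: repeat-"measures ANOVA will be used (group: stimulation/sham X experimental timepoint X before/after surgery"), followed by Tukey-Kramer tests. It does not say which term or contrast estimates the treatment effect, and it names no covariate. General analysis principles mentions covariates only in general terms: "Missing data for baseline covariates to be included in the analysis model will be accounted for using mean imputation for continuous variables".

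On timing, Randomisation procedure says: "Randomisation will occur after the participant has provided informed consent before the surgical procedure is due to start". The Study objectives table lists HRV among the secondary objectives with the label "heart rate variability [explanatory variable"].

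**The concern.** Only the first of the four recordings precedes all stimulation. Treatment cannot have affected it, so any arm difference there is chance. That makes it a true baseline, yet the ANOVA uses it as a level of the outcome.

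With two recordings in a session, the group-by-timepoint contrast for that session equals a two-sample comparison of post-minus-pre change. This fixes the coefficient of the pre-session value at 1, whatever its real relation to the later value. A fitted coefficient removes more noise unless the true slope is 1.

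The group main effect is no better. If only the two post-session recordings responded, each by 0.5 SD, it would estimate (0 + 0.5 + 0 + 0.5)/4 = 0.25 SD.

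This is the only test in the SAP of whether stimulation changes autonomic function, and the trial was not sized for it. Avoidable noise makes a real effect easier to miss.

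**Working it through.** **The plan's own figure.** The SAP gives no SD, correlation or power for HRV. Its only reproducible design figure is for the pain score: "72 patients are required to have a 90% chance of detecting, significant at the 1% level", for a fall "from 34mm in the control group to 23mm in the experimental group after surgery" with SD 12 mm. Per arm, n = 2 × (2.576 + 1.282)² × (12/11)² ≈ 35.4, so 36 per arm and 72 in all, as stated. I use 36 per arm below.

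**Preoperative session.** Let rho be the correlation between the recordings before and after the session, with equal SDs. In units of 2σ²/n:
- change score: 2(1 - rho)
- adjusted for the first recording: 1 - rho²
- ratio: (1 + rho)/2, so the cut is (1 - rho)/2

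Estimating the slope multiplies the adjusted variance by about 1 + 1/(72 - 4) = 1.015.

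| rho (assumed) | change | adjusted | cut | cut after slope cost |
|---|---|---|---|---|
| 0.3 | 1.40 | 0.91 | 35% | 34% |
| 0.5 | 1.00 | 0.75 | 25% | 24% |
| 0.7 | 0.60 | 0.51 | 15% | 14% |
| 0.8 | 0.40 | 0.36 | 10% | 9% |
| 0.9 | 0.20 | 0.19 | 5% | 4% |

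A simulation (36 per arm, 20,000 runs) gave cuts of 34%, 24% and 13% at rho 0.3, 0.5 and 0.7.

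For an assumed effect of 0.5 SD at the two-sided 5% level, noncentral-t power rises from 42% to 59% (rho 0.3), 55% to 68% (0.5) and 77% to 83% (0.7). Charging for the slope gives about 59%, 67% and 83%.

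**Unequal SDs.** With k the post/pre SD ratio, the change-score variance is 1 + k² - 2·rho·k and the adjusted variance is k²(1 - rho²). At rho 0.3, 0.5 and 0.7 the cut is 13%, 4% and 0.2% for k = 1.5, and 58%, 53% and 51% for k = 0.7.

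**Postoperative session.** Let rs be the within-session and rb the between-session correlation (both assumed). The session's own change score has variance 2(1 - rs). Its post recording adjusted for the first, pre-surgery recording has 1 - rb².
- rs 0.5, rb 0.3: 0.91/1.00, a 9% cut
- rs 0.7, rb 0.5: 0.75/0.60, a 25% increase
- rs 0.7, rb 0.3: 0.91/0.60, a 52% increase

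Adding the first recording to the postoperative change score gains nothing in this model: it correlates equally with both postoperative recordings, so its covariance with their difference is rb - rb = 0.

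**Average over both sessions, all correlations equal to rho.** The averaged change score has variance 1 - rho. The two post recordings averaged and adjusted for the first have (1 + rho)/2 - rho² = (1 - rho)(1 + 2·rho)/2. The ratio is (1 + 2·rho)/2: a 20% cut at 0.3, no change at 0.5 and a 20% increase at 0.7.

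**The case against.** Repeated-measures ANOVA is a standard choice for a mechanistic measure. The change score is unbiased for the preoperative session, HRV has no power target, and no statement in the SAP is contradicted. All of that stands, and it limits the point to efficiency on an explanatory measure.

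It is also fair to say that the SAP asks about recordings either side of each session, which suggests an acute within-session response. For the postoperative session, subtracting that session's own pre-recording is then the purpose. This stands too. Replacing it with the first recording would change the question to postoperative level, which mixes carry-over, surgery and the acute response, and could raise the variance. On the other hand, the second pre-session recording follows randomisation and the first session, so the change score there may subtract a carried-over effect. Neither contrast replaces the other.

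Finally, the change-score reading is an inference, because the SAP names no contrast. It holds for the group-by-timepoint term. The missing contrast is itself a reason to amend the text.

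**Conclusion.** The point holds for the preoperative session. The first recording is a true baseline, the planned model does not use it as one, and adjusting for it is never less efficient in large samples. With equal SDs the variance falls by 15% to 35% for rho from 0.7 to 0.3, and by 5% to 10% for rho from 0.9 to 0.8, less about 1.5% for the slope. High correlations are possible for recordings either side of a 50-minute session. The SAP supplies neither rho nor the SDs.

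A reader might infer that the 15% to 35% applies to the whole three-factor ANOVA, or that using the first recording as the covariate throughout costs nothing. The SAP does not support either: its model spans two sessions, only the first has a pre-stimulation baseline, and the gain can become a loss for the second session or the average. Nor should the planned preoperative contrast be read as biased. Severity is minor.

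**What to change.** In the analysis section of the SAP, under Explanatory measures:

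1. Name the treatment contrast for each session.
2. For the preoperative session, estimate the arm difference in the post-session recording adjusted for the first recording, by ANCOVA or the equivalent contrast in a mixed model.
3. For the postoperative session, keep the within-session change as the acute-response contrast. Report the postoperative level adjusted for the first recording as a separate contrast. State that the second pre-session recording follows randomisation and the first session and may carry over its effect.

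The cost is SAP wording and one extra model term, using recordings already planned. Patients without the first recording would come under the mean-imputation rule in General analysis principles.
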